- 6. If a subject prematurely discontinues trial drug, he/she will be asked to remain in the trial, participating in the scheduled trial visits through Week 52. If a subject prematurely discontinues trial drug and does not wish to continue in the trial, he/she will be asked to return for a clinic visit and undergo the Week 52 assessments. Subjects not entering the 52-week **OLE** will return to the clinic 4 weeks after the last dose of trial drug for a Safety Follow-up Visit.
- 7. Informed consent is required prior to performing any assessments, including submission of medical information for central review. Record date and time informed consent was given and who conducted the process on the appropriate source documentation and per required regulations.
- 8. Baseline lung HRCT will be performed only if no previous lung HRCT is available within the last 6 months prior to Screening date. This can be performed any time between the start of the initial 56 days of Screening and must be completed with results from central review vendor prior to Day 1. Confirm enough time for results to be made available from the central review vendor with turnaround time being up to 5 business days for results. Results are required from central review vendor.
- 9. The lung HRCT scan will be performed for all subjects within ±2 weeks of the Week 52/PD Visit. Central review will be performed.
- 10. Histopathology reports used towards IPF diagnosis (if available, but these are not required) will be submitted for central review.
- 11. Subjects will be randomized in a 1:1:1 ratio to receive fipaxalparant (HZN-825) 300 mg QD, fipaxalparant (HZN-825) 300 mg BID, or placebo.
- 12. For subjects who are entering the OLE Phase.
- 13. If SARS-CoV-2 exposure is of clinical concern for any subject, consider using a DLCO up to 6 months before the Screening Visit.
- 14. Perform for WOCBP. Serum pregnancy test at Screening and Week 52 (or as needed). Urine pregnancy tests should also be done every 4 weeks after randomization, which includes both in-clinic testing at scheduled visits prior to dosing (Weeks 1, 4, 16, 28, and 40) and at home (also a ±5-day window) by the subject and reported to the site (Weeks 8, 12, 20, 24, 32, 36, 44, and 48).
- 15. A complete physical examination will be performed, including, but not limited to, cardiac, pulmonary and neurologic assessments.

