- 16. Vital signs (blood pressure, heart rate, respiratory rate, temperature, pulse oximetry) will be measured at each visit.
- 17. Additional electrocardiograms or echocardiograms will be conducted, if clinically indicated. An echocardiogram that has been performed within 3 months prior to Day 1 can serve as the Baseline echocardiogram if the subject has been clinically stable.
- 18. See Section 9.5.5.9 for details.
- 19. For subjects taking warfarin, physicians should monitor their INR, as needed.
- 20. Includes fasting glucose, total cholesterol, high-density lipoprotein cholesterol, low-density lipoprotein cholesterol, and triglycerides.
- 21. HIV testing is optional based on Investigator assessment, institutional practices or local guidelines to rule out suspected HIV or potential for a positive HIV result. Subject consent is required prior to HIV testing.
- 22. Adverse events that occur after signing the informed consent form and prior to dosing on Day 1 will be considered medical history. Adverse events occurring or worsening after the first dose of trial drug through the Safety Follow-up Visit will be considered treatment-emergent adverse events. All adverse events that occur from the signing of informed consent through the Safety Follow-up Visit will be recorded.
- 23. Includes recording of herb/supplement use. See Table 9.1 for restrictions regarding medications.
- 24. PK samples will be collected at each of the following visits: Day 1 (at 2 to 4 hours after the first dose of trial drug), Week 4 (pre-dose), Week 10 (anytime during the visit), Weeks 16 and 28 (pre-dose and 2 to 4 hours post-dose), and Weeks 40 and 52 (pre-dose for subjects entering the 52-week open-label Extension Phase). For the Day 1, Week 16 and Week 28 Visits with post-dose PK samples, the morning dose regimen will be taken in the clinic. Note: all pre-dose samples will be collected prior to any trial drug administration during the clinic visit; record date and time of last dose prior to visit. For subjects not entering the 52-week open-label Extension Phase, a sample will be collected anytime during the Week 52 Visit. Record date/time of all samples.
- 25. To be stored for future analysis. Use of stored serum sample for pharmacodynamic endpoints will be limited to understanding the trial drug as related to investigation of the LPAR1 pathway or disease for the current trial.

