## 9.3.3 Removal of Subjects from Treatment or the Trial

All subjects are free to withdraw from trial participation at any time, for any reason and without prejudice to their further medical care. In addition, the Investigator may terminate a subject from treatment at any time, if further treatment in the trial is not in the best interest of the subject.

If a subject prematurely discontinues trial drug, he/she will be asked to remain in the trial, participating in the scheduled trial visits through Week 52 (if discontinuation occurs during the Core Phase) or Week 104 (if discontinuation occurs during the Extension Phase). If a subject prematurely discontinues trial drug and does not wish to continue in the trial, he/she will be asked to return for a clinic visit and undergo the Week 52 (if discontinuation occurs during the Core Phase) or Week 104 (if discontinuation occurs during the Extension Phase) assessments. Subjects will be asked to return to the clinic for a Safety Follow-up Visit 4 weeks after the last dose of fipaxalparant (HZN-825).

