#### 9.5.5.1.2 Documentation of Adverse Events

Any AEs that occur after signing the ICF and prior to dosing on Day 1 will be considered medical history. The TEAE reporting period begins with administration of the first dose of trial drug on Day 1 and continues until 4 weeks after the last dose of trial drug or premature discontinuation. All medical history, TEAEs and AEs must be recorded in the source documents and on the subject's eCRF. All AEs and SAEs with onset after signing of informed consent through 4 weeks after the last dose of trial drug will be recorded. If a subject discontinues due to an SAE, that subject will be followed as per Section 9.5.5.1.5.

If the Investigator observes an SAE after trial completion that he/she believes was possibly caused by trial drug, the Investigator will report this SAE using the procedures described in Section 9.5.5.1.5. The Investigator is responsible for collecting and documenting the outcome of AEs/SAEs.

If specifically requested, the investigator may need to provide additional follow-up information, such as discharge summaries, medical records, or extracts from the medical records. In this case, all subject identifiers, except for the subject number, will be blinded on the copies of the medical records before submission to the Sponsor.

Detailed information regarding all SAEs must also be recorded on the SAE Reporting Form. Whenever clinically appropriate, the Investigator should group together into a single term the signs and symptoms that constitute a single diagnosis. For example, cough, rhinitis and sneezing might be grouped together as "upper respiratory infection" if the Investigator is confident of the diagnosis.

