# 9.5.5.1.5 Reporting and Documenting Serious Adverse Events

All SAEs beginning with the time of signing of the ICF and continuing through 4 weeks after the last dose of trial drug must be reported. The following steps will be taken to report promptly and document accurately any SAE, whether or not it appears to be related to trial drug:

Report the SAE to the Sponsor by entering the information into the eCRF immediately and not later than 24 hours after becoming aware that a subject has experienced an SAE. If unable to access the eCRF, the event must be reported by submitting the completed SAE Reporting form immediately and not later than 24 hours after becoming aware that a subject has experienced an SAE (see Section 17.1 for contact information).

After the study is completed at a given site, the electronic data capture (EDC) system will be taken off-line to prevent the entry of new data or changes to existing data.

If a site receives a report of a new SAE from a study subject or receives updated data on a previously reported SAE after the EDC system has been taken off-line, then the site can report this information on the paper-based SAE Reporting Form.

- 2. Perform appropriate diagnostic tests and therapeutic measures and submit all follow-up substantiating data, such as diagnostic test reports, hospital discharge summaries and autopsy report to the Sponsor's representative.
- 3. Conduct appropriate consultation and follow-up evaluation until the SAE outcome is known or the SAE is resolved. Outcomes for reported AEs/SAEs/AESIs are to be defined as follows:
  - Recovering/Resolving
  - Recovered/Resolved
  - Not Recovered/Not Resolved
  - Recovered/Resolved with sequelae
  - Fatal
  - Unknown
- 4. All new information for previously reported SAEs must be sent to the Sponsor **immediately and no later than 24 hours** after Investigator's awareness of the new information. If specifically requested, the investigator may need to provide additional follow-up information, such as discharge summaries, medical records, or extracts

from the medical records. Information provided about the SAE must be consistent with that recorded on the Adverse Events eCRF.

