The LCQ total score will be tested in the same manner as that described for the primary analysis of the primary endpoint in Section 6.1.1.1, but based only on observed data. Descriptive statistics for the observed results and change from Baseline in the LCQ total score and each domain score will be summarized for each visit.

6.1.2.6. Time to First Hospitalization Due to Respiratory Distress from Baseline up to Week 52

Hospitalization due to respiratory distress is defined as a non-elective hospitalization lasting more than 24 hours in a hospital, emergency room or observation unit, due to respiratory

Version 2.0

causes that occur after randomization. Adverse events identified as leading to hospitalization due to respiratory distress will be adjudicated to confirm that the event and hospitalization meet the stated criteria.

A Cox proportional hazard model stratified by prior use of approved IPF therapy [yes or no] and FVC% predicted at baseline [\geq 70, <70] and treatment group as factors will provide the hazard ratio, its 90% CI and p-value to compare each HZN-825 group with the placebo group.

A subject will be considered as meeting the event criteria if the adjudication committee identifies any adverse event as leading to hospitalization due to respiratory distress. The start date of the hospitalization will be day of the event. In all other cases, the subject will be considered censored, and their last date of contact in the study (either date of safety follow-up if the subject doesn't enter the extension study or the Week 52 visit date for subjects that enter the extension) will be the date of censoring.

A corresponding Kaplan-Meier plot will be created to supplement the analysis, along with a summary of the quartiles of the Kaplan-Meier time to event estimate.

6.1.2.7. Composite Endpoint: Progression Free Survival (PFS) from Baseline up to Week 52, where Progression Includes Decline in FVC % Predicted ≥ 10% or Death

A Cox proportional hazard model stratified by concomitant use of approved IPF therapy [yes or no] and FVC% predicted at baseline [\geq 70, <70] and treatment group as factors will provide the hazard ratio, its 90% CI and p-value to compare each HZN-825 group with the placebo group.

[figure not shown]

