6.1.3. Exploratory Endpoints

Version 2.0

[figure not shown]

[figure not shown]
6.1.3.6. Time to Death due to Respiratory Deterioration from Baseline up to Week 52

Events of death due to respiratory deterioration will be defined as adverse events with "Does this event represent a respiratory deterioration?" = "Yes" and with an outcome of "Fatal."

An analogous approach as described in Section 6.1.2.6 will be used to analyze this endpoint. If the number of event is rare at the end of the study, a listing will be provided instead of Kaplan Meier or Cox proportional hazard model.

Version 2.0

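### AE/SAE recording closes 4 weeks after the last dose while early stoppers stay to Week 52, so their later respiratory hospitalisations and deaths need not be recorded and may not be counted

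*Protocol*

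**What the plan says.** **Recording window.** Protocol 9.5.5.1.2: "All AEs and SAEs with onset after signing of informed consent through 4 weeks after the last dose of trial drug will be recorded". Protocol 9.5.5.1.5 covers SAEs from signature of the consent form, "continuing through 4 weeks after the last dose of trial drug must be reported". Footnote 22 to the Core Phase schedule: "All adverse events that occur from the signing of informed consent through the Safety Follow-up Visit will be recorded". Protocol 9.3.3 places that visit 4 weeks after the last dose, including for subjects who stop early.

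**Follow-up after an early stop.** Under footnote 6 of the same schedule, a subject who stops trial drug early is kept on: "he/she will be asked to remain in the trial, participating in the scheduled trial visits through Week 52". The schedule grid marks AE assessment at every visit through Week 52 and at the Safety Follow-up Visit. SAP 6.1.1.2 encourages subjects to stay after an intercurrent event, has collection continue to the planned end of the study, and in general applies a treatment policy strategy to the efficacy endpoints.

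**Endpoints built on AE records.** In SAP 6.1.2.6 a subject has a respiratory hospitalisation event "if the adjudication committee identifies any adverse event as leading to hospitalization due to respiratory distress". Otherwise the subject is censored at last contact. The SAP identifies this as the safety follow-up date or, for those entering the Extension, the Week 52 visit. SAP 6.1.3.6: "Events of death due to respiratory deterioration will be defined as adverse events with" a positive answer to the respiratory-deterioration question and a fatal outcome. It is analysed in the same way as 6.1.2.6.

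**A second source for hospitalisation.** Protocol 17.2 collects potential respiratory hospitalisations on a dedicated questionnaire and sends the clinical data to the adjudication committee. Its definition covers events after randomisation and has no 4-week limit.

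**The concern.** Both endpoints run to Week 52, and the general strategy is to count what happens after treatment stops. The written recording rule stops earlier for exactly the subjects that this strategy is meant to keep in. A site that follows 9.5.5.1.2 and 9.5.5.1.5 to the letter would not enter a respiratory admission or death that begins more than 4 weeks after the last dose. A site that follows the schedule grid would enter it. Event ascertainment for a listed secondary objective could then depend on which page a site follows, and it could differ between arms if stopping differs between arms.

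**Working it through.** The plan gives no event rate, stopping rate or power for these two endpoints, so there is no figure of its own to reproduce. The check has three parts.

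**1. One subject traced through the documents.** Trial drug is stopped at Week 20, the subject attends to Week 52, and a respiratory admission or death occurs at Week 35. The window closes at 20 + 4 = Week 24.

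| Place | Is the Week 35 event covered? |
|---|---|
| Protocol 9.5.5.1.2, 9.5.5.1.5 | No |
| Footnote 22, read with Protocol 9.3.3 | No (Safety Follow-up Visit due at Week 24) |
| Schedule grid, AE assessment row | Yes (marked at every visit to Week 52) |
| SAP 6.1.1.2 | Yes |
| Protocol 17.2 | Yes, for a hospitalisation |
| Late-SAE provisions in 9.5.5.1.2 and 9.5.5.1.5 | No: they apply after trial completion or study end, and only to SAEs suspected to be drug-related |

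The AE assessment row that supports collection carries footnote 22, which restates the limit. Hospitalisation has a possible second route through the questionnaire. Respiratory death does not: death is also a recorded reason for leaving the trial (Protocol 9.3.3.2), but that record does not carry the respiratory-deterioration flag that SAP 6.1.3.6 requires.

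**2. Weeks outside the window.** For a subject who stops at week w and stays to Week 52:

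uncovered weeks = max(0, 52 − (w + 4)) = max(0, 48 − w)

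| Stop at week | Uncovered weeks | Share of 52 weeks |
|---|---|---|
| 4 | 44 | 85% |
| 12 | 36 | 69% |
| 26 | 22 | 42% |
| 40 | 8 | 15% |
| 48 or later | 0 | 0% |

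Assumption: stop times are uniform over 52 weeks and all stoppers stay to Week 52. The mean is 48² / (2 × 52) = 2304 / 104 = 22.2 weeks, or 42.6% of 52 weeks. If a fraction d of an arm stops early, the uncovered share of that arm's planned person-time is d × 0.426. This gives 4.3%, 8.5%, 12.8% and 17.0% for assumed d of 10%, 20%, 30% and 40%.

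**3. What the analysis does with those weeks.** This depends on the censoring date.

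- *Early stoppers who enter the Extension.* Protocol 9.3.2.1 allows this for stops not due to safety or tolerability. They are censored at the Week 52 visit, so uncovered weeks count as event-free time at risk.
- *Early stoppers who stay but do not enter.* If censored at the safety follow-up, about week w + 4, the uncovered weeks drop out. With equal constant hazards the expected hazard ratio stays at 1.00, but follow-up that a treatment policy analysis would use is discarded.
- *Subjects who leave the trial.* There is no later trial follow-up for the window to remove.

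If every uncovered week were counted as event-free time at risk, with a true rate ratio of 1 and a constant hazard, the recorded active/placebo ratio would be

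(1 − 0.426 × d_active) / (1 − 0.426 × d_placebo)

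- 20% v 10% stopping: 0.915 / 0.957 = 0.96
- 30% v 10%: 0.872 / 0.957 = 0.91
- 40% v 10%: 0.830 / 0.957 = 0.87
- equal stopping: 1.00

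**The case against.** A reader might infer that later events in early stoppers are lost. The documents do not support that. The grid keeps AE assessment going to Week 52, Protocol 9.3.3.1.1 keeps subjects who stop for lack of efficacy under scheduled safety assessments to Week 52, SAP 6.1.1.2 expects continued collection, and the 17.2 questionnaire has no 4-week cut-off. The grid also prints the Safety Follow-up Visit at Week 56, so footnote 22 could be read as covering the whole Core Phase, although 9.3.3 ties that visit to the last dose. This objection stands against a claim of certain loss. It does not remove the conflict, because 9.5.5.1.2 and 9.5.5.1.5 still set the narrower rule in plain terms.

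A reader might also take 0.91 as the expected bias, favouring the arm that stops more. It is not: it applies only where uncovered weeks are at risk and event-free, and the stopping rates are assumed.

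Nor do the documents support the inference that late drug-related harm goes uncaptured. SAEs suspected to be drug-related are reportable even after the trial ends, and subjects who stop for an AE are followed to resolution or stabilisation.

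Finally, the stakes are limited. One endpoint is an other secondary and one is exploratory, both lie outside the testing hierarchy in SAP 3.4, and SAP 6.1.3.6 replaces the model with a listing if events are rare. That stands, and it limits the weight of the point.

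**Conclusion.** The concern holds as a contradiction on event collection. The written window excludes AEs and SAEs that begin more than 4 weeks after the last dose, while other passages imply that they are collected. Under the window, a late respiratory hospitalisation or respiratory death need not be recorded and may not be counted. The gap is clearest for respiratory death; for hospitalisation, the questionnaire may capture some events.

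For a subject who stays to Week 52, the exposure is 48 − w weeks. That follows from the text alone. The person-time shares and ratios rest on assumed stopping rates, uniform stop times, a constant hazard and full retention, so the size and direction of any bias are unknown.

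The primary and key secondary endpoints use FVC, and PFS uses FVC visit dates and the date of death, so none of them depends on AE records. The same wording governs the Extension to Week 104, where the summaries are descriptive. This should be corrected, but it does not threaten the main conclusion of the trial.

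**What to change.** - In Protocol 9.5.5.1.2, 9.5.5.1.5 and footnote 22, record and report AEs and SAEs to the later of 4 weeks after the last dose and the subject's last visit in that phase (Week 52 or Week 104 for those who stay). At a minimum, do this for respiratory hospitalisations and for all deaths, with cause and the respiratory-deterioration flag.
- Keep the 28-day TEAE definition in SAP 7.1.5, so that the TEAE tables do not change.
- In SAP 6.1.2.6, and in 6.1.3.6 which follows it, set the censoring date at the end of event collection, so that subjects are at risk only while events are being recorded.
- Have sites complete missing AE, hospitalisation and death entries for early stoppers before Core Phase database lock.

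The cost is a protocol clarification, a site memo and a short SAP edit. No visits are added, because AE assessment is already on the grid to Week 52. The downside is a few more off-drug AE and SAE entries.

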# 9.5.5.1.3 Intensity or Severity of Adverse Events

All AEs, both serious and non-serious, will be assessed for severity using the Rheumatology Common Toxicity Criteria v2.0 [Woodworth et al., 2007]. The scale displays Grades 1 through 4 with unique clinical descriptions of severity for each AE (including abnormal laboratory values) based on this general guideline.

- Grade 1 (mild) asymptomatic or transient, short duration (<1 week), no change in lifestyle, no medication or over-the-counter drugs
- Grade 2 (moderate) symptomatic, duration 1 to 2 weeks, alter lifestyle occasionally, medications give relief (may be prescription), trial drug continued

Fipaxalparant (HZN-825)
Protocol: HZNP-HZN-825-303
Version 5.0, Amendment 4

- Grade 3 (severe) prolonged symptoms, reversible, major functional impairment, prescription medications/partial relief, hospitalized <24 hours, temporary trial drug discontinuation or/and dose reduced
- Grade 4 (includes life-threatening) at risk of death, substantial disability, especially if permanent, hospitalized >24 hours, permanent trial drug discontinuation

# 9.5.5.1.4 Relationship or Causality to Trial Drug

The investigator is obligated to assess the relationship between investigational product(s) and each occurrence of each AE and SAE.

Relatedness means that there are facts or reasons to support a relationship between investigational product and the event.

The investigator will use clinical judgment to determine the relationship.

Alternative causes, such as underlying disease(s), concomitant therapy, and other risk factors, as well as the temporal relationship of the event to study treatment administration will be considered and investigated.

The investigator will also consult the Investigator's Brochure and/or product information, for marketed products, in their assessment.

For each AE/SAE, the investigator must document in the medical notes that they have reviewed the AE/SAE and has provided an assessment of causality.

There may be situations in which a SAE has occurred and the investigator has minimal information to include in the initial report. However, it is very important that the investigator always assess causality for every event before the initial transmission of the SAE data.

The investigator may change their opinion of causality in light of follow-up information and send a SAE follow-up report with the updated causality assessment.

The relationship of the trial drug to each AE will be determined by the Investigator and the Sponsor based on the following definitions:

- Not related: There is no plausible temporal relationship or there is another explanation that unequivocally provides a more plausible explanation for the event.
- Related: There is evidence in favor of a causal relationship (i.e., there is a plausible time course) and at least one of the following criteria apply:
  - There is a reasonable pharmacological relationship (or known class effect).
  - There is no other more plausible explanation.

Fipaxalparant (HZN-825) Protocol: HZNP-HZN-825-303 Version 5.0, Amendment 4

- There is a positive de-challenge (without active treatment of the event).
- There is a positive re-challenge.
- There is a distinguishable dose effect.

